6.4.3.3 Analysis of Subject Characteristics

We will evaluate the relationship between iCanCope module use, patterns, gender and change in coping skills and outcomes. Rate and time of specific module use will be evaluated, and LMM will be used to evaluate the relationship between minutes using specific module categories with corresponding change in coping skills efficacy in those categories

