3.2 Purpose of Study/Potential Impact

We expect individuals with NF1 utilizing the iCanCope program to have decreased pain severity and interference if they regularly engage in the program. In addition, due to the added contingency management, we expect to see differences between the intervention groups (*iCanCope-NF* and *iCanCope-NF +CM*). By adding contingencies to increased engagement the CM grouping should have more improvements in pain intensity and pain interference in addition to current iCanCope processes. If we demonstrate initial feasibility and preliminary impact, in collaboration with Drs. [name] and [name], a definitive RCT will be conducted. In future studies, evaluating the sustainability of impact on the outcomes over the course of 12 months is critical to sustaining the impact of the application as well as generalization of treatment. Thus, following the patients in a 1, 3 and 6-month follow-up post-treatment is necessary.

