4.1 Hypothesis

We hypothesize that by customizing the CBT and the MBAA in the mobile application for adults with NF1, individuals will engage regularly, thus acquiring a new set of skills to facilitate their own pain self-management, while pain will decrease.

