6.2 Assessments

6.2.1 Efficacy

All psychometric measures (see appendix) will be evaluated at intake, discharge, follow-up. All of these measures have evidence of reliability and validity in adults in this age range and include target specific measures of NF1 have recommended in previous trials. The **primary research** question is what is the feasibility of the *iCanCope-NF* program? We define feasibility as (1) rates of accrual and dropout, daily logins, engagement, and outcome measures completed and (2) perceptions regarding intervention acceptability and satisfaction; and what are the levels of engagement. logins, with the intervention? The **secondary questions** are: (1) how does the *iCanCope-NF* program compare with the control condition in differences of pain and pain-related activity limitations, sleep functioning, emotional functioning (depression, anxiety), opioid usage, pain catastrophizing, self-efficacy, respondent burden (i.e. Physical Functioning, R, Vitality, Social Functioning, Role-Emotional, and Mental Health), and psychological flexibility immediately post-treatment (T2), (2) does the *iCanCope-NF + CM* increase the engagement of the *iCanCope-NF* program as compared to *iCanCope-NF* without CM, and do their corresponding levels of pain and pain-

related activity decrease with CM?, and (3) do individuals with NF1 utilize the MBAA to help reduce pain symptoms? We hypothesize that by customizing and including MBAA to the program for adults with NF1, that individuals who engage regularly as seen through Analytics Platform for Evaluating Effective Engagement (APEEE) application, will acquire new sets of skills to facilitate pain management, while pain as reported with the Brief Pain Inventory will decrease.

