6.3 Study Procedures

6.3.1 Study Schedule

A total of three visits (all virtual) will be completed. The three visits will consist of admission, discharge and follow-up. Admission for control group will consist of 30 minutes, while admission for individuals within the experimental groups, should take 60 minutes. Discharge evaluations for each should be 45 minutes (30 minutes for assessments, 15 minutes debriefing). Follow-up should be 30 minutes for assessments. Individuals who have access to the mobile application are encouraged to provide daily check-in evaluations (estimated time of 2 minutes) and utilize the different modules at their discretion. The participants will have free reign of the mobile application and are not required to spend any time on the mobile application. No other communication with the research team will take place between all participants and the time intervals previously mentioned. For individuals who are placed in the control group, they will be encouraged to utilize the materials found on several chronic pain websites, with no required time commitments. The mobile application will not remind or notify the participant if they have to login or input information.

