6.4.4 Subsets and Covariates

N/A

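### The usage model in 6.4.3.3 relates self-chosen minutes to change without baseline adjustment, so it cannot support the claim that engagement builds skills and lowers pain

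*Combined protocol and SAP*

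**What the plan says.** **The hypothesis runs through engagement.** Section 4.1 expects that "individuals will engage regularly, thus acquiring a new set of skills to facilitate their own pain self-management, while pain will decrease". Section 6.2.1 expects that "individuals who engage regularly as seen through Analytics Platform for Evaluating Effective Engagement (APEEE) application, will acquire new sets of skills". Section 3.2 expects "decreased pain severity and interference if they regularly engage in the program".

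**The usage analysis.** Section 6.4.3.3 opens broadly: "We will evaluate the relationship between iCanCope module use, patterns, gender and change in coping skills and outcomes". Its one stated model is narrower: "LMM will be used to evaluate the relationship between minutes using specific module categories with corresponding change in coping skills efficacy in those categories".

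**How minutes arise.** Under 6.3.1 participants "utilize the different modules at their discretion", and "The participants will have free reign of the mobile application and are not required to spend any time on the mobile application". Under 6.1.1, use in the contingency management (CM) arm also earns gift cards worth up to 50 dollars.

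**Adjustment.** Section 6.4.3.3 names gender but no baseline score and no arm term. The section headed "6.4.4 Subsets and Covariates" is marked not applicable. The covariate screen in 6.4.1 concerns balance between randomised conditions, not who chooses to use the app.

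**Randomised comparisons.** Section 6.4.3.2 compares app with control on pain and other scores, including self-efficacy and psychological flexibility. It also compares app+CM with app on usage, pain and pain-related activity. For the second comparison it offers only a contrast of nominal data and simple qualitative work.

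**The concern.** The null hypothesis of the usage model is that minutes and change are unrelated. That differs from the statement that engagement has no effect. People who are more motivated, less ill or already improving may both use the app more and report more change. The slope would then be non-zero for an inert app. The bias can also run the other way: if sicker participants use the app more, a real benefit could be hidden.

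Coping skills are the middle step of the stated chain, and 6.4.3.3 contains the only stated model linking an individual's use to change in skills. Nothing there marks the result as exploratory or as an association only. Section 3.2 makes a definitive trial depend on initial feasibility and preliminary impact, so the plan should say whether a usage slope may count towards that.

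**Working it through.** **Plan's own figure.** None exists for this analysis, and the power analysis in 6.4.2 gives no effect size, SD or target power to reproduce. The only input taken from it is 36 per group, hence 36 + 36 = 72 app users. Section 6.4.2 presents 36 as the size after 20% attrition, so no further loss is deducted.

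**Assumptions (not in the documents).** A two-sided 5% test. Minutes have no effect on change. One unmeasured trait U has correlation a with minutes and b with change.

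**Step 1: correlation produced by U alone.** With unit variances, minutes = aU + √(1−a²)·e and change = bU + √(1−b²)·f, with e and f independent. Then ρ = corr(minutes, change) = ab.

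**Step 2: rejection probability (Fisher z).** With z = atanh(ρ)·√(n−3) and √(72−3) = 8.307, the rejection probability is Φ(z−1.96) + Φ(−z−1.96).

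| a = b | ρ | z | Fisher z | Simulation, 20,000 runs |
|---|---|---|---|---|
| 0 | 0 | 0 | 5.0% | 5.0% |
| 0.3 | 0.09 | 0.75 | 11.6% | 11.9% |
| 0.4 | 0.16 | 1.34 | 26.8% | 26.9% |
| 0.5 | 0.25 | 2.12 | 56.4% | 57.1% |

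Raising minutes in the CM arm by an assumed 0.5 SD hardly alters this: 11.4%, 25.7% and 54.4% for the three confounded rows.

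**Step 3: the randomised contrast on the same simulated data.** App+CM versus app, 36 per arm, rejects 4.9% to 5.4% of the time in these four settings. The simulation gave CM no direct effect on scores and had no dropout.

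**Step 4: what that contrast can detect.** Power ≈ Φ(d·√(36/2) − 1.96), with d in units of the SD of the analysed score.
- d = 0.5: 0.5 × 4.243 = 2.12, and Φ(0.16) = 56%.
- d = 0.66: 0.66 × 4.243 = 2.80, and Φ(0.84) = 80%.

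Baseline adjustment reduces the residual SD by an amount the documents do not let one compute.

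**Limits.** The calculation uses one overall correlation. Section 6.4.3.3 matches minutes to change within module categories, which the calculation does not represent.

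**The case against.** Several stronger readings are tempting, and the documents do not support them.

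- *A reader might infer that the trial's hypothesis is tested only through the usage model.* No section names 6.4.3.3 as the hypothesis test. It sits under subject characteristics and speaks of a relationship. Section 6.4.3.2 plans two randomised comparisons that include pain.
- *That the model tests pain.* The LMM concerns coping skills efficacy. Pain could enter only through the word outcomes in the preceding sentence.
- *That a positive slope would trigger the definitive trial.* Section 3.2 does not mention such a slope. The gap is only that the plan does not exclude that use.
- *That the test will reject falsely.* It can reject above 5%. The correlations are assumed, and confounding of the opposite sign could mask an effect.
- *That adding covariates cures the problem.* Arm and baseline score do not remove an unmeasured trait, except so far as they capture it.
- *That the CM contrast is immune.* It tests the incentive to engage. As a test of engagement it keeps 5% only if CM acts on scores through engagement and dropout is not differential. Payment could affect self-report directly. Section 2.1 presents CM as a retention aid, 6.3.6 does not survey those who withdraw, and 6.4.5 codes missing data as zero.

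These points narrow the concern. They leave standing that usage is self-chosen, that no baseline adjustment is stated for the usage model, and that the randomised comparison closest to engagement has no usable model and omits coping skills.

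**Conclusion.** The concern holds in a limited form. The minutes-change slope is an observational association and cannot support the step from engagement to skills and pain. The rejection rate of about 12% to 56% at a nominal 5% illustrates the size for 72 users and assumed trait correlations of 0.3 to 0.5. It is not an estimate for this trial.

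The randomised comparison that bears most closely on engagement is already in the plan but underspecified. It is the better basis for causal statements, although it is imprecise: at 36 per arm, a null result would say little about differences well below 0.66 SD.

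**What to change.** **In 6.4.3.2:** analyse app+CM versus app as randomised, with a baseline-adjusted model of the continuous pain and coping-skills scores, and rest causal statements about engagement on that contrast. Name the coping-skills score, since the outcome lists in 5.2 do not. State that the contrast tests the incentive to engage, that 36 per arm gives 80% power only for about 0.66 SD, and that reading it as a test of engagement requires CM to act through engagement and dropout not to differ by arm.

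**In 6.4.3.3:** include the baseline score in the minutes-change LMM. Report it with and without arm, because conditioning on arm removes the randomised part of the variation in minutes. Label it exploratory and associational, and state that it will not be used as evidence of preliminary impact.

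**Cost:** SAP wording, one specified model and one added covariate. Section 6.3.6 repeats the intake assessments at discharge, so baseline values for those scores are already collected. The price is a weaker claim from the usage data and reliance on a less precise randomised contrast.

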6.4.3.4 Interim Analysis (if applicable)

N/A

6.4.3.5 Health economic evaluation, if applicable

N/A

6.4.3.6 Other

N/A

6.4.4 Subsets and Covariates

N/A

6.4.5 Handling of Missing Data

Another set of automatic email reports, sent on a weekly or less frequent basis, provides a set of designated recipients (e.g., the PI) with information about study logistics, such as number of subjects enrolled, number of subjects active in the protocol, gender composition of the sample, percentage of missing data by each assessment instrument, or any other information necessary to monitor the progress of the project and the compliance with the protocol. A fully computerized system allows this type of monitoring without furnishing investigators with data that could influence the outcome of the study. We will evaluate different assumptions about missing data and code it as zero.

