5.2 Outcome Variables

5.2.1 Primary Outcome Variables

Primary Outcome Measure:

1. Engagement Activity

Total minutes logged on the mobile application will be evaluated between the two groups using the mobile application.

[Time Frame: through the completion of the study, on average 4 months.]

2. Pain Severity

A comparison within groups change of pain severity measured by the Brief Pain Inventory-Short Form. Respondents rate items on a 0-10 scale to indicate the pain severity and interference, and the total score is the mean of each subfactor. The higher the score indicates more severity and interference of pain.

[Time Frame: through the completion of the study, on average 4 months.]

3. Pain Interference Index

A comparison within groups change of pain interference measured by the Pain Interference Index Scale. Respondents rate items on a 0-6 scale to indicate how much pain has interfered with various activities, and the total score is the mean of the six items. Where 6 indicates high interference.

[Time Frame: through the completion of the study, on average 4 months.]

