6.3.6 End of Study and Follow Up

At the end of the study, all participants in each group (TAU, iCanCope, iCanCope+CM) will be required to complete the identical set of assessments at intake, minus demographic information. Individuals who prematurely left early or who withdrawn from the study will not be asked to complete the end of the study survey. Additionally, individuals with access to the iCanCope mobile application license will end and will not be able utilize the mobile application until the follow-up is complete. For individuals who did not have access to the iCanCope mobile application they will continue not having access to the mobile application.

All participants in each group will complete a 6-week post discharge follow-up. The follow-up will be identical to the discharge evaluation. Individuals will be emailed a secured email by the research assistant to complete the survey one day before the 6-week survey. All participants will have a one-week (7days) to complete the assessment, and a reminder email will be sent on the last day of the survey to the participants. Individuals will not be required to complete but will be encouraged to do so.

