6.4.2 Sample Size Considerations

An a priori power analysis conducted through G*Power (Universität Kiel, v. 3.1.9.2) estimated a conservative sample size analysis for the RCT. We are expecting a total of 140 participants, given the length of the trial, we estimate 20% attrition rate of the final sample, giving us a total sample of (n=36) per group, for a final sample size of 108. The power analysis is based on previously utilized research in which estimated effect sizes ranged from 20 to 40 individuals per group (52). We will attempt to enroll equal numbers of male and female individuals to evaluate gender differences through urn randomization process.

52. Hancock, G. R. and R. O. Mueller, Eds. (2010). *The Reviewer's Guide to Quantitative Methods. Power Analysis*. New York, NY, Routledge.

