6.4.3.2 Secondary Objectives Analyses, if applicable

Secondary analyses will explore three research questions: (1) Does smartphone program (*iCanCope-NF*) compared with control condition lead to differences in pain and pain-related activity limitations, sleep functioning, emotional functioning (depression, anxiety), pain catastrophizing, self-efficacy, knowledge, psychological flexibility immediately post-treatment (T2)? This will be evaluated by incorporating an estimating equation approach to understand the differences in scores and using a sequential multilevel logistic regression models to estimate the independent and combined effects of proposed time-varying (contextual) variables on the probability of pain levels. We will also test interaction effects between stable/trait-level participant characteristics and contextual variables. (2) Does the *iCanCope-NF + CM* increase the usage of the *iCanCope-NF* program as compared to *iCanCope-NF* without CM, and do their corresponding levels of pain and pain-related activity decrease? This will be evaluated between the two intervention groups and using the difference in nominal data sets, and simple qualitative analyses. (3) Do individuals with NF1 utilize the MBAA more readily because they are on the mobile application? To assess the moderation effect, we will include an interaction term for each separate moderator variable and key predictor of interest (two-way interaction between moderator and group for cross-sectional analysis and three-way interaction between moderator, group and time for longitudinal analysis) in the regression models and test its significance using Wald t-test.

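### Coding missing scores as zero records every missing pain score as no pain, so dropout alone produces a pain reduction and unequal dropout can create or hide an arm effect

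*Combined protocol and SAP*

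**What the plan says.** Section 6.4.5 describes automatic monitoring reports and then gives the rule: "We will evaluate different assumptions about missing data and code it as zero". It names no alternative assumption and does not limit the rule to any variable, item or visit.

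Section 5.2.1 lists two pain scales as primary outcomes. For the BPI-SF: "Respondents rate items on a 0-10 scale to indicate the pain severity and interference, and the total score is the mean of each subfactor", and "The higher the score indicates more severity and interference of pain". For the Pain Interference Index: "Respondents rate items on a 0-6 scale to indicate how much pain has interfered with various activities", with 6 the worst. The BPI-SF contrast is "A comparison within groups change of pain severity measured by the Brief Pain Inventory-Short Form", and the interference index is worded the same way. Section 6.4.3.2 adds a between-arm question as a secondary analysis: whether the app "compared with control condition lead to differences in pain and pain-related activity limitations".

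On how much will be missing, Section 6.4.2 says "we estimate 20% attrition rate of the final sample". Section 6.3.6 says "Individuals who prematurely left early or who withdrawn from the study will not be asked to complete the end of the study survey" and makes completion of the 6-week follow-up voluntary.

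Nothing else in the document overrides the zero rule. Section 6.4.3.1 mentions a Cox regression in connection with missing data but does not say what happens to a missing pain score. The mixed models are specified for engagement (6.4.3.1) and module use (6.4.3.3), not for pain, and would not help once zeros had been entered as if observed.

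**The concern.** On these questionnaires zero is an answer, and its meaning changes from scale to scale:

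- **BPI-SF (0-10) and Pain Interference Index (0-6):** zero is the best score, so a missing value counts as complete relief.
- **CPAQ-Revised and the 0-100 quality-of-life scales:** zero is the worst score, so a missing value counts as the poorest outcome.
- **PIPS items (1-7), GAD-7 items as coded here (1-4) and FFMQ facets (minimum 7 or 8):** zero cannot occur.

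One rule therefore pushes outcomes in opposite directions. It also reaches single skipped items: the Pain Interference Index is a mean of six items, so one blank coded zero lowers an otherwise uniform score by one sixth.

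Two conclusions are at stake. The within-group pain change would show improvement in any arm that loses people, including control. The comparison between arms would favour whichever arm loses more. Section 2.1 presents contingency management as a way to raise engagement and retention, so unequal dropout is foreseeable. If the app arms keep people better, the rule works against them.

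**Working it through.** **The plan's own figures.** Section 6.4.2 goes from 140 participants to 108 with 20% attrition. 140 × 0.8 = 112 and 108 / 0.8 = 135, so the figures do not quite agree; 140 to 108 implies 1 − 108/140 = 22.9%. This is a separate minor point. I use 20% and note 22.9%.

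**Inputs from the document.** Scale ranges and directions (5.2.1); 20% attrition (6.4.2); alpha 0.05, taken as two-sided (6.4.1); about 140/3 = 47 randomised per arm; BPI interference of at least 3 at entry (5.3.2).

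**Assumptions, because the document gives no values.** BPI mean 4, 5 or 6; SD 1.5 or 2.0; correlation between baseline and post-treatment 0.6; dropout unrelated to pain.

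**Step 1: bias in one arm.** If a share d is coded zero and those people would have averaged m, the arm mean moves by −d × m. With d = 0.20 this is 0.8, 1.0 or 1.2 points for m = 4, 5 or 6. At 22.9% it is 0.91, 1.14 or 1.37.

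For BPI interference, a lower bound needs no assumed mean. If the entry score serves as baseline, each zero-coded person falls by at least 3, so the arm falls by at least 0.2 × 3 = 0.6 even if completers do not change.

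**Step 2: how often a within-arm test is falsely significant.** Hand check at m = 5, SD 2, d = 0.2:
- Completers' change has variance 2 × 4 × (1 − 0.6) = 3.2.
- Zero-coded people change by minus their baseline: mean −5, variance 4.
- Overall variance = 0.8 × 3.2 + 0.2 × 4 + 0.8 × 0.2 × 25 = 7.36, so SD = 2.71.
- Standard error = 2.71/√47 = 0.396, and the expected t is about 1.0/0.396 = 2.5 against a critical value of about 2.0. That implies rejection in roughly 70% of trials.

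Simulation (4,000 trials per scenario, scores limited to 0-10, t-tests on change) gives 73% for this case.

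**Step 3: no true effect, full range.** Percentages run from SD 2.0 to SD 1.5.

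| Missing, arm A / arm B | Result | Mean 4 | Mean 5 | Mean 6 |
|---|---|---|---|---|
| 20% / 20% | false fall in each arm | 0.8 | 1.0 | 1.2 |
| 20% / 20% | false significant within-arm fall | 61-73% | 73-83% | 80-88% |
| 25% / 15% | false arm difference | 0.4 | 0.5 | 0.6 |
| 25% / 15% | type I error | 13-15% | 14-17% | 15-18% |
| 30% / 10% | false arm difference | 0.8 | 1.0 | 1.2 |
| 30% / 10% | type I error | 37-45% | 44-53% | 50-56% |

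The false arm difference is (dA − dB) × m and favours the arm with more missing. The nominal rate for a false within-arm fall is 2.5%. With equal dropout the between-arm type I error stays at 4.4% to 5.0%. Analysing only observed values on the same data held it at 3.9% to 5.6% in every null scenario.

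**Step 4: a true 1-point benefit (mean 5, SD 2).** Power is 77% with no dropout.

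| Missing, app / control | Expected difference, by arithmetic | Simulated | Power in the right direction | Observed values only |
|---|---|---|---|---|
| 20% / 20% | 0.8 × (−1) = −0.80 | −0.78 | 31% | 66% |
| 15% / 25% | (0.85×4 − 5) − (0.75×5 − 5) = −0.35 | −0.33 | 9% | 65% |
| 10% / 30% | (0.90×4 − 5) − (0.70×5 − 5) = +0.10 | +0.13 | under 2% | 66% |

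In the last row the estimate changes sign. The small gaps between arithmetic and simulation come from limiting scores to 0-10.

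**The case against.** **Leavers may not be in the analysis.** No analysis population is defined, and Section 6.4.2 calls the 108 the final sample size. If leavers are excluded, zeros touch only gaps among those retained. With 36 per arm and an assumed 3% to 5% residual missing, false within-arm reductions occur in about 5% to 10% of trials and the between-arm error stays near 5%. This reading is possible, but no section states it, and excluding leavers has a bias of its own.

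**The sentence is ambiguous.** Zero may have been meant for logins and minutes, where it can be sensible, or as one of several assumptions. The text says neither.

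**The tests and alpha differ from the plan.** Section 6.4.3.2 assigns the between-arm pain question to estimating equations and multilevel logistic models, and Section 6.4.1 promises multiplicity corrections. With 45 per arm (36/0.8) and SD 2, the uncorrected rates are 60-79% within arm, 12-16% at 15% against 25% missing, and 35-47% at 10% against 30%. A Bonferroni correction over three primary outcomes (my assumption) lowers these to 39-58%, about 5-8% and about 20-31%. The bias in points does not change, and a different model fitted to the same zeros inherits it.

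**Unequal dropout is not established.** The incentives reward app use rather than survey completion, controls are offered the app afterwards, and the 10% against 30% split is illustrative. This stands. The within-arm bias and the loss of power do not depend on it.

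**Pain is not consistently primary.** Section 6.2.1 makes feasibility the primary question and pain secondary. That is true, but Section 5.2.1 lists pain as primary, and the error affects pain under either label.

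**Conclusion.** The rule is wrong as written. Following Section 6.4.5 literally with the plan's own 20% attrition moves mean BPI pain down by 0.2 times its mean, or 0.8 to 1.2 points for means of 4 to 6, with no treatment effect. It weakens a real effect even when dropout is equal, and can reverse it when the control arm loses more people.

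The direction follows from the scales alone. The sizes rest on the assumed means, SDs and correlation, on dropout unrelated to pain, on uncorrected tests, and on leavers being analysed. Error rates were worked out on the 0-10 scale only; on the 0-6 Pain Interference Index the same proportional fall applies, but its error rates were not computed. Equal dropout does not inflate between-arm type I error.

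**What to change.** In Section 6.4.5:

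- Remove zero coding for all questionnaire scores. Missing scores stay missing, and each instrument's rule for skipped items is stated.
- Define the analysis set as all randomised participants.
- Analyse pain with a likelihood-based mixed model over the planned assessments, or with multiple imputation using baseline score, gender, arm and app usage.
- Add one sensitivity analysis that is unfavourable to dropouts, such as a delta shift towards worse scores. Carrying the baseline forward could be added, but it assumes no change rather than worsening.
- Keep zero only for app minutes and logins actually recorded as no use during the 8-week access period.

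The observed-values results above look good because dropout was simulated as unrelated to pain. The sensitivity analysis covers the case where it is not.

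In Section 6.3.6, send the discharge and 6-week surveys to every randomised participant who has not refused further contact, whatever their app use.

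The cost is a rewording of two sections, a little more analysis and some extra survey emails. Contacting leavers changes a study procedure, so it needs an amendment approved by the IRB and the funder (Sections 7.2 and 7.13). The interventions and sample size stay as they are.
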